6.0 CRITERIA FOR SUBJECT ELIGIBILITY

6.1 Subject Inclusion Criteria

- 1. Be willing and able to provide written informed consent/assent for the trial.
- 2. Histologically- or cytologically- confirmed CRC.
- 3. Metastatic or recurrent CRC.

- 4. Subjects have received two or more standard available therapies known to prolong survival and for which they would be considered eligible. Such therapies should include regimens containing oxaliplatin and irinotecan in combination with a fluoropyrimidine if appropriate (e.g., FOLFOX and FOLFIRI or their variants).
- 5. At least one tumor for which palliative RT is considered appropriate standard therapy (cohort 1); or, at least one tumor for which palliative ablation is considered appropriate standard therapy (cohort 2).
- 6. At least one index lesion that will not undergo RT or ablation, and which is measurable based on RECIST 1.1.
- 7. Be ≥ 18 years of age on day of signing informed consent.
- 8. Consent for tumor biopsies and blood draws for research purposes.
- 9. Consent for use of available archived tissue for research purposes.
- 10. Have a performance status of 0 or 1 on the ECOG Performance Scale.
- 11. Demonstrate adequate organ function as defined in Table 6.1, all screening labs should be performed within 6 weeks of treatment initiation.

Table 6.1 Adequate Organ Function Laboratory Values

0	II -h
System	Laboratory Value
Hematological	
Absolute neutrophil count (ANC)	≥1,500 /mcL
Platelets	≥100,000 / mcL
Renal	
Serum creatinine	≤1.5 X upper limit of normal (ULN)
OR	OR
Measured or calculated ^a creatinine	
clearance (GFR can also be used in	≥60 mL/min for subject with creatinine levels > 1.5 X
place of creatinine or CrCl)	institutional ULN
Hepatic	
Serum total bilirubin	≤ 1.5 XULN OR
	Direct bilirubin ≤ ULN for subjects with total bilirubin levels >

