	1.5 ULN
AST (SGOT) and ALT (SGPT)	≤ 2.5 XULN OR
AST (SGOT) and ALT (SGPT)	≤ 5 X ULN for subjects with liver metastases
Coagulation	
International Normalized Ratio (INR) or	≤1.5 X ULN unless subject is receiving anticoagulant therapy
` '	as long as PT or PTT is within therapeutic range of intended
Prothrombin Time (PT)	use of anticoagulants
Activated Partial Thromboplastin Time	≤1.5 X ULN unless subject is receiving anticoagulant the rapy
•	as long as PT or PTT is within therapeutic range of intended
(aPTT)	use of anticoagulants
^a Creatinine clearance should be calcula	ted per institutional standard.

- 12. Female subject of childbearing potential should have a negative serum pregnancy within 2 weeks prior to starting radiation therapy or undergoing ablation.
- 13. Female subjects of childbearing potential should be willing to use 2 methods of birth control or be surgically sterile, or abstain from heterosexual activity for the course of the study through 120 days after the last dose of study medication (Reference Section 9.5.2). Subjects of childbearing potential are those who have not been surgically sterilized or have not been free from menses for > 1 year.
- 14. Male subjects should agree to use an adequate method of contraception starting with the first dose of study therapy through 120 days after the last dose of study therapy.

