8.0 PRETREATMENT EVALUATION

To be completed prior to starting RT or ablation and within 6 weeks of starting pembrolizumab:

- CT scan with contrast (chest, abdomen and pelvis). If patient is unable to receive CT contrast, or the abdominal/pelvic target lesion is indeterminate on CT scan then MRI with contrast (abdomen and pelvis) plus CT chest without contrast may be perfromed. Noncontrast CT CAP may be used if the target lesion(s) do not require contrast for accurate measurements.
- 12-lead Electrocardiogram (EKG).
- Signed informed consent for study participation.
- History and physical examination, including height, weight, vital signs (temperature, pulse rate, respiration rate, blood pressure), and performance status (ECOG).
- Serum pregnancy test for all women of childbearing potential (within two weeks of starting RT or ablation). If the test result is positive related to pregnancy, the patient will not be allowed to participate in this study.
- CBC with differential and platelet count, serum chemistries (Na, Cl, BUN, Creatinine, K, CO2, and glucose), LFTs (AST, ALT, alkaline phosphatase, total bilirubin), calcium, albumin, total protein, and CEA
- Serology for HepBsAg, HepBcAb and hepatitis C antibody (negative test acceptable prior to screening period)
- Blood test for research purposes.
- Perform baseline tumor biopsy for research purposes at the time of fiducial placement or ablation or during a separate procedure.

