9.0 TREATMENT/INTERVENTION PLAN

9.1 Dosing Instructions and Schedule

Drug	Dose/	Dose	Route of	Regimen/	Use
	Potency	Frequency	Administration	Treatment Period	
Pembrolizumab	200 mg	Q3W	IV infusion	n/a	Experimental

The first day of dosing is considered Day 1. Subjects will receive pembrolizumab as an IV infusion. Refer to "MK-3475 Drug Preparation Instructions" manual.

Trial treatment should be administered on Day 1 of each cycle. Trial treatment may be administered up to 3 days before or after the scheduled Day 1 of each cycle due to administrative reasons. All trial treatments will be administered on an outpatient basis.

Pembrolizumab will be administered as a 30 minute IV infusion (every effort should be made to target infusion timing to be as close to 30 minutes as possible. However, given the variability of infusion pumps from site to site, a window of -5 minutes and +10 minutes is permitted (i.e., infusion time is 30 minutes: -5 min/+10 min).

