10.0 EVALUATION DURING TREATMENT/INTERVENTION

Study Calendar

Period	Screening						Trea	tment			End of
Cycle ¹	4C	1	1	2	2	3	4	5	6	7+	study
Week	<6 weeks ²	0	1	3	4	6	9	12	15	18+	visit ¹⁵
Informed consent	Х										
Medical history	Х										
EKG	Х										
CT/MRI ³	х						х			х	х
Height ⁴	Х										
Physical examination	Х	Х		Х		Х	Х	Х	Х	х	Х
Vital signs/ Performance status ⁴	Х	х		х		Х	Х	Х	Х	х	х
Report medications	Х	х		х		Х	Х	х	Х	х	х
Pulse oximetry		Х		Х		Х	Х	Х	Х	х	Х
Report side effects				х		Х	Х	Х	Х	х	Х
CBC ^{5,6}	Х	Х		х		Х	Х	Х	Х	х	Х
Comp ^{5,7}	Х			х		Х	Х	Х	Х	х	Х
Thyroid function (TSH, fT3,fT4)	х					х		х		odd cycles	
CEA ⁸	х	х					х			х	х
Hepatitis B and C ⁹	Х										
Pregnancy test if female (Serum) ¹⁰	Х										
Research blood tests 5,11	Х			х		Х	Х				
Obtain archived tissue ¹²	Х										
Research tumor biopsy ¹³	Х		Х		х						
RT (Cohort 1) ¹⁴	Х										
Ablation (Cohort 2) ¹⁴	Х										
Pembrolizumab		х		х		х	х	х	х	х	

- 1. Each cycle is approximately 3 weeks in duration, corresponds to 1 completed treatment.
- 2. Procedures must be performed within 6 weeks prior to dose 1 of Pembrolizumab on Day 1.
- 3. CT or MRI will be performed during screening, then at 9 week (±1 wk) intervals and at final visit if more than 4 weeks from prior imaging. If patient is unable to receive CT contrast or the abdominal/ pelvic target lesion is indeterminate on CT then MRI with contrast (abdomen and pelvis) plus CT without contrast (chest) may be performed. Imaging may be delayed up to 2 weeks if patient is receiving additional RT or ablation.
- 4. Vital signs to include heart rate, respiratory rate, blood pressure, and weight.
- 5. Blood to be collected prior to dosing any study medications.
- 6. Hematology to include standard complete blood cell (CBC) panel.
- 7. Comprehensive metabolic panel included sodium, potassium, chloride, bicarbonate, BUN, creatinine, glucose, total protein, albumin, bilirubin, alkaline phosphatase, AST, ALT, calcium.
- 8. CEA to be obtained during screening, day 1 and then within two weeks (or on day) of subsequent imaging.
- 9. Serology for HepBsAg, HepBcAb and hepatitis C antibody (unless previously tested negative).
- 10. Serum pregnancy test is required within 2 weeks of starting radiation or ablation

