- 11. Blood draws for research purposes performed during screening or day 1, then weeks 3, 6 and 9 for all patients. Additional blood draws beyond week 9 are permitted based upon interesting clinic/immunological findings for all patients.

- 12. Up to 20 x 5µm slides (unstained) of archived tissue will be requested on all patients for research purposes. For patients undergoing routine procedures during the study, additional tissue (up to 20 x 5µm slides (unstained)) may be obtained from each routine procedure. for research purposes.
- 13. Research tumor biopsy will be performed during fiducal placement or ablation or during a separate procedure, then 1 week (±3 days) after completing RT or ablation (from the radiated/ablated lesion) and 4 weeks after dose #1 of pembrolizumab (±1 week) from a non-ablated/radiated lesion. For patients that are unable to have biopsy 4 weeks after dose #1 of pembrolizumab, the procedure may be delayed up until Week 9.
- 14. RT begins or ablation is performed during cycle 1, within one week prior to dose 1 of Pembrolizumab.
- 15. EOS visit occurs 4(±1 wk) weeks after last dose of pembrolizumab. CT scan or MRI to be done only if last imaging was conducted greater than four weeks prior to the date of the Final Visit.

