A separate guidance document has been provided entitled "event of Clinical Interest and Immune-Related Adverse Event Guidance Document." This document provides guidance regarding identification, evaluation and management of ECIs and irAEs. Additional ECIs are identified in this guidance document and also need to be reported to the Sponsor within 5 calendar days to the MSKCC Safety Office and to Merck Global Safety according to the ECI reporting guidance (APPENDIX C).

Subjects should be assessed for possible ECIs prior to each dose. Lab results should be evaluated and subjects should be asked for signs and symptoms suggestive of an immune-related event. Subjects who develop an ECI thought to be immune-related should have additional testing to rule out other etiologic causes. If lab results or symptoms indicate a possible immune-related ECI, then additional testing should be performed to rule out other etiologic causes. If no other cause is found, then it is assumed to be immune-related.

ECIs that occur in any subject from the date of first dose through 90 days following cessation of treatment, or the initiation of a new anticancer therapy, whichever is earlier, whether or not related to the Merck"s product, must be reported within 5 calendar days to the MSKCC Safety Office and to Merck Global Safety according to the ECI reporting guidance (APPENDIX C).

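### No metabolic panel is scheduled at week 0, so the last required liver and renal values before dose 1 predate RT or ablation and may be six weeks old

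*Combined protocol and SAP*

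**What the plan says.** Section 8.0 places the pretreatment work-up, which includes serum chemistries and liver function tests, before local treatment: "To be completed prior to starting RT or ablation and within 6 weeks of starting pembrolizumab". Note 2 of the Section 10.0 calendar gives the same limit ("Procedures must be performed within 6 weeks prior to dose 1 of Pembrolizumab on Day 1"), and so does inclusion criterion 11 in Section 6.1 ("all screening labs should be performed within 6 weeks of treatment initiation"). Calendar note 14 fixes the order of local treatment and drug: "RT begins or ablation is performed during cycle 1, within one week prior to dose 1 of Pembrolizumab".

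The liver and renal tests sit in the calendar's Comp row, defined in note 7: "Comprehensive metabolic panel included sodium, potassium, chloride, bicarbonate, BUN, creatinine, glucose, total protein, albumin, bilirubin, alkaline phosphatase, AST, ALT, calcium". That row is marked at screening, at weeks 3, 6, 9, 12, 15 and 18+, and at the end-of-study visit. It is blank at week 0, when the first pembrolizumab dose is given. CBC, CEA, physical examination, vital signs and pulse oximetry are all marked at week 0.

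The Events of Clinical Interest text in Section 17.2 applies to every dose: "Subjects should be assessed for possible ECIs prior to each dose. Lab results should be evaluated". Section 9.1, on dosing, names no chemistry panel for day 1.

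**The concern.** Followed as written, the calendar lets dose 1 be given after ablation, or after RT has begun, with no hepatic or renal result from after that local treatment started. A change caused by ablation, by RT or by progressing disease in the preceding weeks would first appear at week 3, when the patient has already had one dose.

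That matters for how events are recorded and attributed:

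- Section 11.1.1 makes the first dose the dividing line between medical history and adverse events, and asks the investigator to rate each event's relation to the study drug.
- Section 17.2 treats an ECI as immune-related when additional testing finds no other cause.
- Section 11.1.3 exempts a hepatic abnormality from recording as an adverse event if it reflects a pre-existing condition that has not worsened. Judging that needs a recent pre-drug value.
- Eligibility overlaps part of the hepatic ECI. Table 6.1 accepts AST and ALT "≤ 5 X ULN for subjects with liver metastases", while the AST/ALT component of the ECI begins at 3 x ULN. Some eligible patients may therefore already be past that component before any drug is given.

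Safety and tolerability is the first secondary objective in Section 2.0, so the quality of this baseline bears on a stated aim.

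**Working it through.** **Step 1: which dosing visits have a panel.** The calendar has 11 columns. The relevant rows read:

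| Row | Screening | 0 | 1 | 3 | 4 | 6 | 9 | 12 | 15 | 18+ | End of study |
|---|---|---|---|---|---|---|---|---|---|---|---|
| Pembrolizumab | | x | | x | | x | x | x | x | x | |
| CBC | x | x | | x | | x | x | x | x | x | x |
| Comp | x | | | x | | x | x | x | x | x | x |
| CEA | x | x | | | | | x | | | x | x |

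Pembrolizumab is marked in 7 columns. CBC covers 7 of 7 and Comp covers 6 of 7; the only dosing column without Comp is week 0. The column alignment can be checked on CEA: note 8 calls for it at screening and day 1, and the row is marked in exactly those two columns before the imaging visits.

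**Step 2: age of the last required panel at dose 1.** The plan's own limit is 6 weeks (calendar note 2; criterion 11). 6 x 7 = 42 days. Section 8.0 also requires this panel before RT or ablation starts, so it never reflects any effect of local treatment.

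**Step 3: first panel after local treatment starts.** Local treatment starts 0 to 7 days before dose 1 (note 14), and the next panel is at week 3, nominally day 21 after dose 1.

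- Nominal: 21 + 0 = 21 days to 21 + 7 = 28 days.
- With the window in Section 9.1 ("Trial treatment may be administered up to 3 days before or after the scheduled Day 1 of each cycle due to administrative reasons"): 21 - 3 + 0 = 18 days to 21 + 3 + 7 = 31 days.

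**Step 4: longest permitted gap between consecutive required panels.** From screening to week 3: 42 + 21 = 63 days, or 42 + 21 + 3 = 66 days with the window. At later dosing visits the interval is about 21 days.

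**Step 5: does other text require a day 1 panel?**

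- Section 4.2 calls for routine blood tests every three weeks. The week 0 CBC and CEA already satisfy that sentence.
- Section 4.2 also spells out routine blood work as CBC, COMP and CEA, but for follow-up visits after 24 months of treatment.
- Sections 8.0, 9.1 and 17.2 do not name a day 1 metabolic panel.

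The gap therefore stands on the text. How many patients would have an abnormal value at week 0 cannot be computed from the documents.

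**The case against.** The strongest reply is that this is a missed tick and not a decision. Comp is marked at every other dosing visit, CBC and CEA are drawn at week 0, and the only place that expands routine blood work includes COMP. That is quite likely, and sites may draw the panel anyway. But the calendar is what sites follow, and nothing else in the text requires the panel. A single mark lost when the table was converted to text cannot be strictly excluded. The CEA check confirms column positions, not every cell, so the cell should be compared with the source calendar.

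Second, the ECI instruction has little force at dose 1. Reportable ECIs run from the first dose, immune-related ones cannot precede the drug, and the wording does not strictly demand a same-day panel. This stands: the week 0 blank is not a direct breach of Section 17.2. It does not remove the value of a reference drawn just before the period in which ECIs begin to count.

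Third, the hepatic ECI also needs bilirubin of at least 2 x ULN with alkaline phosphatase below 2 x ULN, so raised transaminases alone do not trigger it. That is correct, and the overlap concerns one component. Table 6.1 does, however, admit total bilirubin above 1.5 x ULN when direct bilirubin is within normal limits, with no stated cap on the total.

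Fourth, a screening value always exists, and 42, 63 and 66 days are permitted maxima, not expected intervals. In the RT cohort radiation may continue after dose 1, so a week 0 value separates the effects only in part. All of this stands. The appendix guidance on ECIs is listed by title only, so the conclusion is limited to the text available.

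**Conclusion.** The concern holds. The calendar requires a metabolic panel at 6 of the 7 dosing columns and omits it at week 0. The last required liver and renal values before dose 1 always predate RT or ablation and may be up to 42 days old. The first values after local treatment starts come 21 to 28 days later (18 to 31 with the dosing window), after one dose of drug. The schedule applies to all 18 to 48 patients.

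The consequence is confined to first-dose safety review and to the baseline for attributing hepatic and renal events. The attribution gain would be mainly in the ablation cohort and partial in the RT cohort. The response endpoint, the Simon boundaries and the error rates are untouched. The conclusion rests on reading the blank week 0 cell as intended content; if it is a clerical omission, the correction is the same. It should be made because it is cheap and specific, although it is not critical to the trial's main result.

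**What to change.** Mark Comp at week 0 in the Section 10.0 calendar. Specify that the sample is taken before dosing, with the blood already drawn for CBC and CEA, and that the result is reviewed before dose 1 is given. State that this value, alongside the screening value, is the pre-drug reference for later hepatic and renal abnormalities.

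With this change the number of dosing visits without chemistry falls from one to none. The liver and renal values at dose 1 come from the same visit, after ablation or the start of RT.

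The cost is one chemistry panel per patient, 18 to 48 in total, and the wait for the result before the first infusion. No extra visit or venepuncture is needed.

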18.0 INFORMED CONSENT PROCEDURES

Before protocol-specified procedures are carried out, consenting professionals will explain full details of the protocol and study procedures as well as the risks involved to participants prior to their inclusion in the study. Participants will also be informed that they are free to withdraw from the study at any time. All participants must sign an IRB/PB-approved consent form indicating their consent to participate. This consent form meets the requirements of the Code of Federal Regulations and the Institutional Review Board/Privacy Board of this Center. The consent form will include the following:

- 1. The nature and objectives, potential risks and benefits of the intended study.
- 2. The length of study and the likely follow-up required.
- Alternatives to the proposed study. (This will include available standard and investigational therapies. In addition, patients will be offered an option of supportive care for therapeutic studies.)
- 4. The name of the investigator(s) responsible for the protocol.

5. The right of the participant to accept or refuse study interventions/interactions and to withdraw from participation at any time.

Before any protocol-specific procedures can be carried out, the consenting professional will fully explain the aspects of patient privacy concerning research specific information. In addition to signing the IRB Informed Consent, all patients must agree to the Research Authorization component of the informed consent form.

Each participant and consenting professional will sign the consent form. The participant must receive a copy of the signed informed consent form.

20.0 APPENDICES

APPENDIX A: Requisition For Blood Specimens
APPENDIX B: Requisition For Biopsy Specimens

APPENDIX C: PEMBROLIZUMAB PROGRAM (MK-3475) EVENT OF CLINICAL

INTEREST GUIDANCE DOCUMENT, Version 5.0

APPENDIX A: REQUISITION FOR BLOOD SPECIMENS

Single Arm Phase II Study to Assess the Efficacy of Pembrolizumab Plus Radiotherapy or Ablation in Metastatic Colorectal Cancer Patients

A) Section A: Patient information (To be completed by RSA)	B) Section B: Sample information (To be checked off by RSA)
Patient initials: Patient study ID#: Site:	4 CPT tubes (10 cc) will be collected at the following time points []Baseline []Week 3 []Week 6 []Week 9 []Week
C) Section C: Sample Collection information (To be completed by phlebotomy) Drawn By: Date/ Time:	Sample Collection Instructions: 1. Gently invert all tubes 8-10 times at room temperature immediately after collection 2. Write patient initials, date, and time of collection on each tube 3. Place all collected tubes in biohazard ziplock bag 4. Send all specimens at room temperature via Stat Messengers to
D) Section D: Sample Processing information (To be completed by laboratory personnel) Lab ID#: Received by: Date/Time:	
E) Section E: Sample shipping information (To be completed by laboratory personnel) Sent by: Date/Time: Received by: Date/Time:	Sample shipping Instructions Ship samples on dry ice to: [name] Memorial Sloan-Kettering Cancer Center Zuckerman Research Building [name]
Date/Time:	

APPENDIX B: REQUISITION FOR BIOPSY SPECIMENS OR LEFT OVER TISSUE OBTAINED DURING A ROUTINE PROCEDURE

Single Arm Phase II Study to Assess the Efficacy of Pembrolizumab Plus Radiotherapy or Ablation in Metastatic Colorectal Cancer Patients

A) Section A: Patient information	B) Section B: Sample information
•	,
(To be completed by RSA)	(To be checked off by RSA)
Patient initials:	[] Baseline: 5 Core Biopsies
Patient study ID#:	[] Week 1: 5 Core Biopsies
Patient study ID#:	[] Week 1. 3 cole biopsies
Site:	[] Week 4: 5 Core Biopsies
 	
	[] Routine Procedure: 5 Cores or divided tumor
	[] reduite recodule. S Solds of divided tailler
C) Section C: Sample Collection information	Sample Collection Instructions:
(To be completed by physician or designee)	1. Cores # 1, 2, 5: Place into formalin (3-5 cc)
(10 20 completed by physician or designed)	
01/1 15	2. Cores # 3, 4: Place in sterile Nunc tube and snap
Obtained By:	freeze in liquid nitrogen
Procedure:	
1 1000dd10.	3. Core #: Place in RPMI (5 cc)
D / /T'	
Date/ Time:	
	[[6.4]]
	[If tissue remains, collect/ process as for core #5]
D) Section D: Storage/Processing information	Sample Starage/ Processing Instructions
D) Section D: Storage/Processing information	Sample Storage/ Processing Instructions
D) Section D: Storage/Processing information (To be completed by laboratory personnel)	1. Cores # 1, 2, 5: Store at 4-8°C
· ·	1. Cores # 1, 2, 5: Store at 4-8°C
(To be completed by laboratory personnel)	
· ·	 Cores # 1, 2, 5: Store at 4-8°C Cores # 3, 4: Store at -70 to -80°C
(To be completed by laboratory personnel) Lab ID#:	 Cores # 1, 2, 5: Store at 4-8°C Cores # 3, 4: Store at -70 to -80°C Core #: Process immediately for isolation of
(To be completed by laboratory personnel)	 Cores # 1, 2, 5: Store at 4-8°C Cores # 3, 4: Store at -70 to -80°C
(To be completed by laboratory personnel) Lab ID#:	 Cores # 1, 2, 5: Store at 4-8°C Cores # 3, 4: Store at -70 to -80°C Core #: Process immediately for isolation of
(To be completed by laboratory personnel) Lab ID#: Received by:	 Cores # 1, 2, 5: Store at 4-8°C Cores # 3, 4: Store at -70 to -80°C Core #: Process immediately for isolation of
(To be completed by laboratory personnel) Lab ID#:	 Cores # 1, 2, 5: Store at 4-8°C Cores # 3, 4: Store at -70 to -80°C Core #: Process immediately for isolation of
(To be completed by laboratory personnel) Lab ID#: Received by: Date/Time:	 Cores # 1, 2, 5: Store at 4-8°C Cores # 3, 4: Store at -70 to -80°C Core #: Process immediately for isolation of tumor infiltrating lymphocytes.
(To be completed by laboratory personnel) Lab ID#: Received by:	 Cores # 1, 2, 5: Store at 4-8°C Cores # 3, 4: Store at -70 to -80°C Core #: Process immediately for isolation of tumor infiltrating lymphocytes. Sample shipping Instructions
(To be completed by laboratory personnel) Lab ID#: Received by: Date/Time: E) Section E: Sample shipping information	 Cores # 1, 2, 5: Store at 4-8°C Cores # 3, 4: Store at -70 to -80°C Core #: Process immediately for isolation of tumor infiltrating lymphocytes. Sample shipping Instructions
(To be completed by laboratory personnel) Lab ID#: Received by: Date/Time:	 Cores # 1, 2, 5: Store at 4-8°C Cores # 3, 4: Store at -70 to -80°C Core #: Process immediately for isolation of tumor infiltrating lymphocytes. Sample shipping Instructions Ship samples 1, 2, and 5 at room temperature;
(To be completed by laboratory personnel) Lab ID#: Received by: Date/Time: E) Section E: Sample shipping information (To be completed by laboratory personnel)	 Cores # 1, 2, 5: Store at 4-8°C Cores # 3, 4: Store at -70 to -80°C Core #: Process immediately for isolation of tumor infiltrating lymphocytes. Sample shipping Instructions
(To be completed by laboratory personnel) Lab ID#: Received by: Date/Time: E) Section E: Sample shipping information	 Cores # 1, 2, 5: Store at 4-8°C Cores # 3, 4: Store at -70 to -80°C Core #: Process immediately for isolation of tumor infiltrating lymphocytes. Sample shipping Instructions Ship samples 1, 2, and 5 at room temperature; samples 3 and 4 on dry ice, attention:
(To be completed by laboratory personnel) Lab ID#: Received by: Date/Time: E) Section E: Sample shipping information (To be completed by laboratory personnel) Sent by:	 Cores # 1, 2, 5: Store at 4-8°C Cores # 3, 4: Store at -70 to -80°C Core #: Process immediately for isolation of tumor infiltrating lymphocytes. Sample shipping Instructions Ship samples 1, 2, and 5 at room temperature; samples 3 and 4 on dry ice, attention: [name]
(To be completed by laboratory personnel) Lab ID#: Received by: Date/Time: E) Section E: Sample shipping information (To be completed by laboratory personnel)	 Cores # 1, 2, 5: Store at 4-8°C Cores # 3, 4: Store at -70 to -80°C Core #: Process immediately for isolation of tumor infiltrating lymphocytes. Sample shipping Instructions Ship samples 1, 2, and 5 at room temperature; samples 3 and 4 on dry ice, attention:
(To be completed by laboratory personnel) Lab ID#: Received by: Date/Time: E) Section E: Sample shipping information (To be completed by laboratory personnel) Sent by:	 Cores # 1, 2, 5: Store at 4-8°C Cores # 3, 4: Store at -70 to -80°C Core #: Process immediately for isolation of tumor infiltrating lymphocytes. Sample shipping Instructions Ship samples 1, 2, and 5 at room temperature; samples 3 and 4 on dry ice, attention: [name] Memorial Sloan-Kettering Cancer Center
(To be completed by laboratory personnel) Lab ID#: Received by: Date/Time: E) Section E: Sample shipping information (To be completed by laboratory personnel) Sent by:	 Cores # 1, 2, 5: Store at 4-8°C Cores # 3, 4: Store at -70 to -80°C Core #: Process immediately for isolation of tumor infiltrating lymphocytes. Sample shipping Instructions Ship samples 1, 2, and 5 at room temperature; samples 3 and 4 on dry ice, attention: [name] Memorial Sloan-Kettering Cancer Center Zuckerman Research Building
(To be completed by laboratory personnel) Lab ID#: Received by: Date/Time: E) Section E: Sample shipping information (To be completed by laboratory personnel) Sent by: Date/Time:	 Cores # 1, 2, 5: Store at 4-8°C Cores # 3, 4: Store at -70 to -80°C Core #: Process immediately for isolation of tumor infiltrating lymphocytes. Sample shipping Instructions Ship samples 1, 2, and 5 at room temperature; samples 3 and 4 on dry ice, attention: [name] Memorial Sloan-Kettering Cancer Center Zuckerman Research Building [name]
(To be completed by laboratory personnel) Lab ID#: Received by: Date/Time: E) Section E: Sample shipping information (To be completed by laboratory personnel) Sent by:	 Cores # 1, 2, 5: Store at 4-8°C Cores # 3, 4: Store at -70 to -80°C Core #: Process immediately for isolation of tumor infiltrating lymphocytes. Sample shipping Instructions Ship samples 1, 2, and 5 at room temperature; samples 3 and 4 on dry ice, attention: [name] Memorial Sloan-Kettering Cancer Center Zuckerman Research Building
(To be completed by laboratory personnel) Lab ID#: Received by: Date/Time: E) Section E: Sample shipping information (To be completed by laboratory personnel) Sent by: Date/Time:	 Cores # 1, 2, 5: Store at 4-8°C Cores # 3, 4: Store at -70 to -80°C Core #: Process immediately for isolation of tumor infiltrating lymphocytes. Sample shipping Instructions Ship samples 1, 2, and 5 at room temperature; samples 3 and 4 on dry ice, attention: [name] Memorial Sloan-Kettering Cancer Center Zuckerman Research Building [name]
(To be completed by laboratory personnel) Lab ID#: Received by: Date/Time: E) Section E: Sample shipping information (To be completed by laboratory personnel) Sent by: Date/Time: Received by:	 Cores # 1, 2, 5: Store at 4-8°C Cores # 3, 4: Store at -70 to -80°C Core #: Process immediately for isolation of tumor infiltrating lymphocytes. Sample shipping Instructions Ship samples 1, 2, and 5 at room temperature; samples 3 and 4 on dry ice, attention: [name] Memorial Sloan-Kettering Cancer Center Zuckerman Research Building [name]
(To be completed by laboratory personnel) Lab ID#: Received by: Date/Time: E) Section E: Sample shipping information (To be completed by laboratory personnel) Sent by: Date/Time:	 Cores # 1, 2, 5: Store at 4-8°C Cores # 3, 4: Store at -70 to -80°C Core #: Process immediately for isolation of tumor infiltrating lymphocytes. Sample shipping Instructions Ship samples 1, 2, and 5 at room temperature; samples 3 and 4 on dry ice, attention: [name] Memorial Sloan-Kettering Cancer Center Zuckerman Research Building [name]
